2.0 Objectives

Directions: Describe the purpose, specific aims or objectives. Be sure to also include the hypothesis being tested. The purpose of this study is to characterize sleep health (quantity, quality, timing, variability), diabetes-self-management, symptoms (general diabetes and emotional), and glycemia (glycemic control and glucose variability) over 7 days in young adults age 18-25 years with type 1 diabetes (T1D) during the COVID-19 pandemic. Aim 1. Determine the prevalence of clinically significant emotional distress, diabetes distress, high-risk sleep apnea, and clinically significant insomnia in 200 young adults with T1D and compare to the prevalence of the general T1D population pre-pandemic. Aim 2. Examine the associations between sleep health, diabetes self-management, symptoms, and glycemia in 200 young adults with T1D. Aim 3. Determine the additional contribution of sleep (quantity, quality, timing, or variability) to the variance in symptoms, diabetes self-management, and glycemia in 200 young adults with T1D. Aim 4. Elicit feedback on a behavioral sleep self-management intervention from 10 young adults with T1D who are at low risk for sleep apnea and do not meet the threshold for clinically significant insomnia.

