3.0 Background

Directions: Describe the relevant prior experience and gaps in current knowledge describing how it will add to existing knowledge. Include any relevant preliminary data.

Type 1 Diabetes (T1D) affects 1.6 million Americans, and only 14% of emerging adults age 18-25 years achieve targets for glycemic control (glycosylated hemoglobin A1C <7.0%) based on national data. Lower A1C levels are associated with reduced risk for both micro- and macrovascular complications, better neurocognitive function, and better diabetes quality of life. Emerging adults with T1D experience frequent sleep interruptions at night, demonstrate less time in slow wave sleep, have a more pronounced sleep extension on weekends, and report sleep that is of poorer quality and less restorative compared to matched controls. Short sleep (duration < 7 hours) and circadian misalignment (inappropriately timed sleep and wake) are associated with poorer glycemic control in emerging adults with T1D. Both short sleep and circadian misalignment may affect diabetes self-management negatively and result in difficulties in performing activities necessary to optimize glycemic control (e.g., checking glucose, responding to results, calculating and administering insulin doses). Therefore, improving sleep

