5.0 Number of Research Participants

Directions: Indicate the target number of research participants to be accrued locally, and, if this is a multi-site study, indicate the total number of research participants to be accrued across all sites.

Example language that can be used: *We will enroll 25 subjects at CWRU and plan to enroll 150 subjects study wide.* We will enroll 200-300 participants for aims 1-3 and will invite 10-15 participants from aims 1-3 to complete aim 4

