8.0 Recruitment Methods

Note: Attach all applicable recruitment materials to the last section of the Smart form under “Recruitment Materials.”

1. Which of the following methods will be used to recruit research participants? – *Select all that apply*
 - Email
 - Phone call
 - Letter
 - Advertisement (e.g., poster, flyer, etc.)
 - Social media
 - Other. *Please specify:* [Click here to enter text.](#)
2. Describe when, where, and how potential research participants will be recruited.
 A description and link for the study will be posted on the College Diabetes Network site, T1D exchange site, and through social media sites (Facebook, Twitter, Instagram, TuDiabetes). We will also reach out to contacts who have been identified as potential role models to share the pre-approved post on their social media sites. Recruitment will begin once IRB approval has been obtained. Role models will be offered an honorarium of \$10 for their assistance. Messages will direct potential participants to a link in REDCap where they can confidentially fill out a form expressing an interest in the study. We will not advertise on Facebook or other sites as described above without IRB approval of the messages or ad(s). The purpose of the honorarium for role models is that the role model

may not participate in the study per se so would not be eligible for a gift card but may have a following on social media to post the link on. The role model would not receive a finder's fee or identify potential participants. We wanted to offer a one-time honorarium for the role model's time to post the study information. The honorarium is compensation for the role models taking time to share our post and tag the study team. This compensation will not be influential to others, as it is not offered to just any person and is not a part of the advertisement. There should not be any undue influence as we are providing an incentive for participation in our study that is in line with other studies of similar designs. The study is longitudinal over 1 week and it seems that breaking down the incentives with a step wise approach as the PI has used in a previous study may be more successful in recruiting a representative sample.

3. Describe the source (e.g., from what department, EMR, etc.) of the research participants. The two primary sources of recruitment are the aforementioned list community outreach through IRB-approved targeted ads on Facebook.

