16.0 Data Analysis Plan

Directions: Describe the data analysis plan, including any statistical procedures. If applicable, provide a power analysis, and study/safety endpoints. Aim 1: Descriptive statistics will be computed for all demographic and multi-item scales. These variables will be used to describe the sample. Study variables will be examined for marked skewness, outliers and systematic missing data. Cronbach's alphas will be computed for the multi-item scales for the full sample and separately by gender, race/ethnicity, age, and T1D duration. Aims 2-3: Correlations between sleep health, diabetes self-management, and symptoms will be assessed. Variables with a modest relationship ($r \geq .3$) will be included in a linear regression analysis. A linear regression will be run where the IV is diabetes self-management, and the DVs are glycemic control. Possible covariates will be determined. Path analysis will be done to test the mediational hypothesis (sleep health variables or distress (general and diabetes) and physical (diabetes) will mediate the effect of diabetes self-management on glycemic control) the following regression equations will be run (Baron & Kenny, 1986): To test the mediation model, the independent variable (diabetes self-management) must affect the mediator (sleep quantity, quality, or timing) in the first equation; next, the independent variable (diabetes self-management) must affect the dependent variables (glycemic control) in the second equation; and lastly the mediator (sleep quantity, quality, or timing) must affect the dependent variables in the third equation. Mediation is present if the independent variable (diabetes self-management) has no effect when the mediator (sleep quantity, quality, timing) is controlled (Baron & Kenny, 1986). Power analysis: A moderate effect size with two predictors (0.13) and 4-5 covariates would require a sample size of 150-200 participants based on a G*power 3.1 calculation. Aim 4:

We will engage 10 emerging adults and use think-aloud interviews where we will ask participants to think out loud about the program as it is delivered. An RA will prompt them to think out loud and audio record the session. We will code the data for themes using qualitative **content analysis**. The expected outcome of aim 4 is to identify barriers and facilitators of the proposed intervention and a protocol for the next phase of the study.

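### The mediation rule in section 16.0 requires the direct effect to vanish and specifies no indirect-effect estimate or interval, so real partial mediation of about half or less would usually go undeclared

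*Protocol*

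**What the plan says.** Protocol section 16.0, under Aims 2-3, names path analysis and states the hypothesis that "sleep health variables or distress (general and diabetes) and physical (diabetes) will mediate the effect of diabetes self-management on glycemic control". It then lists three regressions in the causal-steps tradition, citing a 1986 paper. Self-management must affect the mediator, the mediator must affect the outcome, and, in between, "the independent variable (diabetes self-management) must affect the dependent variables (glycemic control) in the second equation". The deciding sentence follows: "Mediation is present if the independent variable (diabetes self-management) has no effect when the mediator (sleep quantity, quality, timing) is controlled".

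The section gives no significance level, no equivalence bound for an absent effect, no provision for partial mediation, and no estimate, test or interval for the indirect effect. The hypothesis also covers distress and physical symptoms, but the regression steps name only sleep variables as mediators. The SAP describes a GEE analysis of a two-group pilot intervention and does not mention mediation, so it does not fill the gap. On size, section 5.0 says: "We will enroll 200-300 participants for aims 1-3".

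**The concern.** A direct effect can only be estimated, and an estimate is never exactly zero. Read literally, the deciding sentence can never be satisfied. The reading that can be carried out is that the direct effect is not statistically significant, and this treats a failure to reject as evidence of absence. Partial mediation, where part of the effect runs through sleep and part does not, is then declared only when the test of the direct effect happens to miss. Requiring a significant total effect adds a second way to lose a real indirect path.

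A report of no mediation could therefore mean that there is no indirect path, that there is a real partial one, or that the total effect is weak. No planned interval would tell these apart.

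**Working it through.** **The plan's own figure.** Section 16.0 gives 150-200 participants for an effect size of 0.13 with two predictors and 4-5 covariates. This is a regression calculation, not one for mediation, and it states neither alpha nor power. An omnibus test of 6-7 predictors at f² = 0.13, alpha .05 and 95% power needs 167-176, inside the range; testing two predictors at 80% power needs 78. The figure says nothing about the mediation rule and is not used below.

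**Notation.** a = self-management to mediator; b = mediator to glycemic control, given self-management; c′ = direct effect; c = total effect = c′ + ab.

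**Inputs.** N = 200 and 300 come from section 5.0. Two-sided .05 and standardized normal variables with a = b are assumptions, as are all path sizes.

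**Rule as simulated.** a, c and b are each significant and c′ is not. The comparator is a test of the indirect path: a and b both significant. An interval for ab gives nearly the same rates.

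**Check by hand.** With R² = b² + c′² + 2abc′,

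SE(c′) ≈ √[(1 − R²) / ((N − 3)(1 − a²))].

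For a = b = .3 and c′ = .2: R² = .09 + .04 + .036 = .166.
- N = 200: SE = √[.834 / (197 × .91)] = .068 and c′/SE = 2.93. Against a critical value of 1.97, c′ is significant in about Φ(0.96) = 83% of samples. At most 17% are left for the rule; simulation gives 16%.
- N = 300: SE = √[.834 / (297 × .91)] = .056 and c′/SE = 3.60. c′ is significant in about Φ(1.63) = 95%, leaving 5%; simulation gives about 5%.

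**By share mediated.** Total effect .30, N = 200, a = b = √(share × .30), c′ = (1 − share) × .30:

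| Share mediated | a = b | c′ | c′/SE | c′ not significant (formula) | Rule declares (simulated) | Indirect path detected |
|---|---|---|---|---|---|---|
| 30% | .300 | .210 | 3.09 | 13% | 13% | 98% |
| 50% | .387 | .150 | 2.19 | 41% | 41% | 100% |
| 75% | .474 | .075 | 1.08 | 81% | about 80% | 100% |

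At 30% mediated the three required effects are all significant in 97.3% of samples and the full rule is met in 12.9%. The last clause alone therefore removes 97.3 − 12.9 = 84.4 points. At N = 300 the rule declares 3.5%, 24% and 74% in the three rows. With total effects of .2 and .4 and 75% mediated, it declares about 72% and 69% at N = 200.

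**By fixed paths.** Percentage declared by the rule, N = 200 → N = 300:

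| a = b | c′ = 0 | c′ = .1 | c′ = .2 | c′ = .3 | Indirect path detected |
|---|---|---|---|---|---|
| .2 | 4 → 7 | 17 → 25 | 9 → 4.5 | 0.5 → 0 | 65-68 → 87-90 |
| .3 | 22 → 32 | 47 → 50 | 16 → 5 | 0.5 → 0 | 98-99 → 100 |
| .4 | 60 → 77 | 66 → 57 | 16 → 4 | 0.5 → 0 | 100 → 100 |
| .5 | 91 → 94.5 | 69 → 56 | 14 → 3 | 0.2 → 0 | 100 → 100 |

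**Complete mediation.** With a = b = .3 and c′ = 0, the total effect is .3 × .3 = .09. At N = 200 its expected t is about .09 × √198 / √(1 − .0081) = 1.27, below 1.97. The total effect is non-significant in about 74% of samples, and the rule declares mediation in about 22%. Here the cause is the total-effect condition, not the last clause.

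**Is the comparison fair?** With no indirect effect (a = .3, b = 0, or a = 0, b = .3; N = 200), the test of a and b declares mediation in 4.5-5.2% of samples and the rule in 0-0.7%. The higher detection is not bought with excess false positives. A percentile bootstrap of ab at N = 200 gave 93.4-96.0% coverage and a 5.0% false-positive rate.

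**The case against.** Several stronger readings are tempting, and the documents do not support them.

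- *A reader might infer that a vanished direct effect is the only criterion.* Section 16.0 sets three necessary conditions first, and they matter. With a = b = 0 and c′ = .1 at N = 200, a non-significant direct effect alone would occur in 72% of samples, so without those conditions the rule would over-declare mediation.
- *A reader might infer that the rule misses most partial mediation in general.* The documents give no path sizes, and the result depends on them. With c′ = .05 at N = 200 the rule declares 74% at a = b = .4 and 88% at .5. At a total effect of .2, half mediated is about the tipping point.
- *A reader might infer that recruiting more always makes things worse.* For any non-zero direct effect, detection does fall to zero as N grows without limit. Over 200 to 300, however, some cases improve: a = b = .3 with c′ = .05 rises from 40% to 54%.
- *A reader might infer that the named path analysis cannot give the indirect effect.* It could. The gap is that no such estimate or interval is specified, and that the stated decision does not use one.

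It is also fair to say that mediation is not itself one of the four aims.

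One further uncertainty stands. Section 16.0 says that variables correlated at .3 or more "will be included in a linear regression analysis", without saying whether this screen also gates the mediation equations. The figures above assume that it does not. If it gated the self-management and sleep pair, then at a = b = .3, c′ = .2 and N = 200 the rule would declare 9% and the indirect-path test 49-50%. At a = b = .2 both would be nearly powerless, with the indirect-path test at about 5%.

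What survives is the defect in the decision rule and the size of the loss where half or less of the effect is mediated.

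**Conclusion.** Wrong as written, limited to the mediation hypothesis under Aims 2-3; the prevalence and association results are untouched. That the rule infers absence from non-significance, and that no indirect-effect interval is specified, follows from the text of section 16.0 once the workable reading is accepted. The size of the loss is conditional on assumed standardized paths with a = b, two-sided .05, and no correlation screen on these models. Five independent covariates, counted as lost degrees of freedom only, move the rule's figures by about 1 point.

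Under those assumptions the error runs toward missed effects, not false ones. It is large when about half or less of the effect is mediated and modest when most of it runs through strong paths. The detection rate of 98% or more for the indirect path belongs to the total-effect-.3 cases tabulated by share and to the a = b = .3 cases. With paths of .2 and N = 200 it is 65-68%, still well above the rule.

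**What to change.** In section 16.0, remove two requirements as criteria for mediation: that the direct effect vanish once the mediator is controlled, and that the total effect be significant. For each mediator named in the hypothesis (sleep health variables, general and diabetes distress, physical symptoms), report the indirect effect ab with a 95% bootstrap or Monte Carlo interval. Report the direct and total effects with their intervals alongside. State that the conclusion on mediation rests on the indirect-effect interval, so that partial mediation is reported as such. Say whether the correlation screen applies to these models.

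The cost is a few sentences of protocol text and a standard resampling procedure. No new data are needed.

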duration and timing may be potential therapeutic targets to improve glucoregulation and clinical outcomes (diabetes self-management, diabetes quality of life, neurocognitive function) in this high-risk population. Sleep plays a critical role in physical, mental, social, and emotional health as well as in the effective functioning of the immune system. Short sleep duration is associated with a higher BMI, an impaired body weight regulation and impaired glucose metabolism. COVID-19 has posed barriers for achieving or maintaining healthy sleep. These barriers may include a disruption in daily life, increased anxiety and worry, worsened depression and isolation, a greater family and work stress, and increased screen time. **Preliminary data:** Forty-six young adults with T1D (67.4% female, mean age 22.3 ± 3.2 years, mean BMI 27.0 ± 4.4 kg/m², mean A1C $7.2 \pm 1.1\%$) were recruited from the Yale New-Haven Health System. All study participants (N = 46, 100%) had actigraphy data ranging from 6-14 days/night (Mean 9.0 ± 2.8 days/night) and a majority (n = 43, 93.5 %) had continuous glucose monitor data ranging from 6-14 days/night (Mean 9.5 ± 3.5 days/night). Shorter total sleep time and greater sleep variability were associated with greater daytime sleepiness ($r = -0.47$, $p = .001$ and $r = 0.40$, $p = .005$ respectively). Greater sleep variability was associated with neurocognitive function (longer median reaction time $\rho = 0.31$, $p = .03$ and more lapses $\rho = 0.36$, $p = .01$ on the PVT) and greater glucose variability (mean of daily differences $\rho = 0.33$, $p = .04$). Shorter total sleep time was associated with greater diabetes distress symptoms ($\beta = -0.32$, $p = .032$). Greater sleep variability was associated with greater symptoms of neurological pain ($\beta = 0.32$, $p = .019$) and hypoglycemia ($\beta = 0.32$, $p = .016$). Longer sleep onset latency was associated with greater psychological fatigue symptoms ($\beta = 0.31$, $p = .024$), greater psychological cognitive symptoms ($\beta = 0.37$, $p = .012$), greater hyperglycemia symptoms ($\beta = 0.33$, $p = .024$), and a greater total symptom burden ($\beta = 0.30$, $p = .042$). Poorer sleep efficiency was associated with greater diabetes distress symptoms ($\beta = -0.35$, $p = .018$) and greater hypoglycemia symptoms ($\beta = -0.30$, $p = .027$). The associations between the sleep-wake characteristics and general emotional distress symptoms were not significant. Sex and BMI differences were noted for diabetes symptoms. Specifically, females reported greater hypoglycemia and fatigue symptoms and those with a higher BMI reported greater fatigue, neurological pain, and cardiology symptoms. Associations of these sleep-wake characteristics and symptoms remained statistically significant even after adjustment for sex and BMI.

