27.0 Provisions to Monitor the Data to Ensure the Safety of Research Participants

1. Describe how often the data will be monitored for completeness, accuracy and adherence to the protocol. N/A this is a cross sectional design. Data will be collected once for aims 1-3 and once for aim 4 as this is not a repeated measures design.
2. Indicate if there will be a Data and Safety Monitoring Board or Committee:
 - There will not be a formal Data and Safety Monitoring Board/Committee.
 - There will be a formal Data and Safety Monitoring Board/Committee.

Provide information about the DSMB/C including the contact information of the committee member(s) (as applicable); whether it is independent from the study sponsor; how often it meets; the type of data that will be used; written reports, etc. Click here to enter text.

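### The mediation rule in protocol section 16.0 cannot separate mediation by sleep from confounding by sleep, so meeting it does not justify reporting mediation

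*Protocol*

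**What the plan says.** For Aims 2-3, section 16.0 (Data Analysis Plan) tests mediation by the classical regression steps. The first condition is that "the independent variable (diabetes self-management) must affect the mediator (sleep quantity, quality, or timing) in the first equation". The second is that "the independent variable (diabetes self-management) must affect the dependent variables (glycemic control) in the second equation". The third is that "the mediator (sleep quantity, quality, or timing) must affect the dependent variables in the third equation". The decision sentence follows: "Mediation is present if the independent variable (diabetes self-management) has no effect when the mediator (sleep quantity, quality, timing) is controlled".

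The covariates are left to be determined. No reversed model, common-cause alternative, time-lagged model or interval for an indirect effect is planned.

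The documents describe the timing of measurement in two ways. Section 27.0 says "N/A this is a cross sectional design". Section 8.0 says "The study is longitudinal over 1 week", and section 12.0 has a baseline survey followed by twice-daily surveys for a week. Neither description leads to an analysis that uses the order of the measurements. The SAP describes a two-group pilot analysed by GEE and says nothing about mediation.

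**The concern.** The rule has four parts: three associations and the loss of one of them after adjustment. All are computed from between-person regressions. If sleep drives both self-management and glycemic control, and self-management affects neither, all four parts hold in the population. The crude association between self-management and glycemia is then confounding by sleep, and it disappears once sleep is controlled.

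The protocol itself supplies both arms of that structure. Section 3.0 says "Both short sleep and circadian misalignment may affect diabetes self-management negatively", which is the reverse of the first mediation condition. The same section ties short and badly timed sleep to poorer glycemic control and adds: "Short sleep duration is associated with a higher BMI, an impaired body weight regulation and impaired glucose metabolism". Aim 3 likewise treats sleep as contributing to both self-management and glycemia.

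At stake is the reading of self-management. A finding of mediation says that self-management influences glycemic control by way of sleep. The common-cause reading says that the observed association gives no evidence of such an influence.

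**Working it through.** **The plan's own figure.** Section 16.0 gives no error rate for the mediation rule. Its sample size of 150-200 states neither alpha nor power, so it cannot be reproduced uniquely. Reading 0.13 as R² gives f² = .13/.87 = .149. An omnibus test of 6-7 predictors at alpha .05 then needs 147-154 participants for 95% power and 195-203 for 99%. The figure is attainable but not confirmed, and nothing below rests on it.

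**Inputs.** The rule is from section 16.0. N = 200-300 is from section 5.0, and 150 is the low end of the section 16.0 figure. Assumed: two-sided alpha .05, "no effect" read as p ≥ .05, and standardized paths of .3, .4 and .5. The documents give no correlation of self-management with sleep or with glycemic control.

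**Algebra.** Write X for self-management, M for sleep and Y for glycemia, with a the X-M path and b the M-Y path.

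- Mediation (X → M → Y): r_XM = a, r_MY = b, r_XY = ab.
- Common cause (X ← M → Y): r_XM = a, r_MY = b, r_XY = ab.
- In both, the partial correlation of X and Y given M has numerator r_XY − r_XM·r_MY = ab − ab = 0.

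With normal errors, a rule that uses only these regressions therefore has the same chance of being met under either structure.

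**Simulated rate at which the rule declares mediation (common cause / true mediation), no direct effect:**

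| N | a=b=.3 | a=b=.4 | a=b=.5 |
|---|---|---|---|
| 150 | 16% / 17% | 47% / 47% | 84% / 84% |
| 200 | 22% / 22% | 60% / 59% | 91% / 91% |
| 300 | 32% / 30% | 77% / 77% | 95% / 95% |

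The differences within cells are simulation error. The size is easy to follow at N=200 and paths of .4. Conditions one and three are met almost always, the second in about 63% of runs, and the adjusted effect is non-significant in about 95%: .63 × .95 ≈ .60.

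**Variations at N=200.**

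- *Entry screen.* Applying the r ≥ .3 screen of section 16.0 to sleep and self-management lowers the .3 cell to about 15% and leaves .4 at about 58%. The two structures stay equal.
- *Skewed (exponential) errors.* The two structures stay within about one point: 21% and 21%, 58% and 58%, 90% and 89%.
- *Indirect-effect test instead.* At paths of .3, joint significance of the two paths occurs in 97.7% of runs under mediation and 97.6% under a common cause, so this does not help.
- *Sleep unrelated to the other two.* The rule was never met, so the fault concerns direction and common cause and is not a response to noise.

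**Adding a direct effect c′ of self-management to the common-cause model.** Then r_XY = c′ + ab and r_MY = b + ac′, again identical to mediation with the same direct effect. Rates at N=200, all variables at unit variance:

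| c′ | a=b=.3 | a=b=.4 | a=b=.5 |
|---|---|---|---|
| .1 | 48% | 67% | 69% |
| .2 | 16% | 16% | 13% |
| .3 | <1% | <1% | <1% |

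Other ways of scaling the residual variance move these cells by a few points, so I quote them as about 48-71%, 13-19% and under 1%. A small direct effect raises the rate at .3 and .4 because the second condition is met more often. A larger one makes the adjusted effect significant, and the rule then fails.

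**The case against.** The strongest objection is that the high rates need self-management to have little or no direct effect on glycemia. Section 3.0 describes self-management as the activities needed for good glycemic control, such as checking glucose and dosing insulin, which suggests a real direct path. This stands as a limit on the size: at N=200 a direct effect of .2 brings the rate below 20%, and at N=300 to about 3-6%. It does not restore the rule, because the two structures still cannot be told apart at any direct effect.

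The path sizes are also assumed. The nearest pilot figure in section 3.0 is rho = 0.33, between sleep variability and glucose variability, which are not the variables named in the rule. This too limits the size and not the defect.

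The study calls itself descriptive, and Aims 2-3 speak of associations and variance. That is fair, but section 16.0 still commits to a causal conclusion. The daily surveys might seem to supply time order. However, the documents do not say when self-management is measured, and no planned model uses the order.

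A reader might infer two stronger points that the documents do not support. The first is that a false mediation claim will be reported; it is only possible, at a rate set by unknown paths. The second is that the error would misdirect the Aim 4 intervention. Both structures contain an effect of sleep on glycemia, Aim 4 already concerns a sleep intervention, and its content is refined from interviews, not from the mediation test.

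**Conclusion.** The decision sentence is wrong as written. Meeting its conditions cannot distinguish mediation by sleep from confounding by sleep, and no other part of the protocol or SAP repairs this. The equality is exact for linear normal models with matched paths and held closely with skewed errors.

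The chance of a false declaration is conditional on sleep being a common cause and not a mediator. At N=200 it runs from about 22% to 91% over assumed paths of .3 to .5 with no direct effect, and falls to under 1% with a direct effect of .3. Further covariates would not cure it, because the confounder is the proposed mediator itself. Nor would reversing the order: self-management as mediator would then be confused with self-management as common cause. The consequence is limited to what the study may say about the role of self-management.

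**What to change.** Replace the decision sentence in section 16.0 with wording such as:

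> If these conditions are met we will report that sleep statistically accounts for the association between self-management and glycemic control. Because the data do not order these variables in time, this is equally consistent with sleep being a common cause of both and will not be reported as mediation.

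Beside it, report the sleep-adjusted self-management coefficient with its 95% CI, which also shows how large a direct effect the data leave open.

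A within-person model of nightly sleep and next-day glucose is optional. It depends on shared glucose data whose daily resolution and overlap with the diary week are not stated. It also leaves out self-management, so it would not test the mediation hypothesis.

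The required change is one sentence and one reported interval, with no new data. The downside is that the study gives up the statement that mediation is present.
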